## I. INTRODUCTION

This document describes the planned statistical analyses for ReLeaf, a 14-week, pragmatic randomized, double-blind, four-arm parallel-group trial evaluating the effect of discounted vouchers for: 1) a placebo soft-gel capsule product, 2) high THC: low CBD soft-gel capsule product (4.3 mg THC/0.7 mg CBD), 3) equal THC:CBD soft-gel capsule product (2.5 mg THC/2.5 mg CBD), or 4) low THC: low CBD soft-gel capsule product (0.2 mg THC/4.8 mg CBD) on cumulative opioid analgesic use. The ReLeaf Study randomized participants 1:1:1:1 across four arms.

This Statistical Analysis Plan (SAP) was developed prior to unblinding and database lock.

## II. OBJECTIVES AND HYPOTHESES

- a. **Primary Objective:** To determine whether assignment to the four arms (placebo, high THC:low CBD, equal THC:CBD, low THC:high CBD) results in a difference in cumulative opioid analgesic dose compared to placebo coupon at 14 weeks.
  - i. **Null Hypothesis ( $H_0$ ):** Participants randomized to vouchers for deeply discounted soft-gel capsules containing high THC:low CBD, equal THC:CBD, or low THC:high CBD will experience a greater reduction in opioid dose compared to vouchers for deeply discounted placebo capsules.
  - ii. **Alternative hypothesis:** Opioid dose and adverse events will differ by randomized voucher arm.
- b. **Secondary Objectives:** We will also measure outcomes with strong associations with cannabis or opioid analgesic use, including pain, substance use, symptoms of mental illness, and potential adverse events). Secondary analyses will be considered exploratory.

## III. STUDY DESIGN AND RANDOMIZATION

This study is a pragmatic, double-blind, randomized, parallel-group controlled trial.

- a. Allocation ratio: Participants are allocated 1:1:1:1 to each arm.
- b. Randomization method: Block randomization to ensure equal randomization over time. We stratified by history of cannabis use (cannabis naïve, non-daily cannabis use, daily cannabis use), baseline opioid use (chronic opioid use versus sporadic opioid use), and primary pain condition (neuropathic versus non-neuropathic pain). Chronic opioid treatment is defined as prescribed opioids for greater than or equal to 90 overlapping days in the past 182 days.
- c. Blinding: Participants, investigators and outcome assessors are blinded to allocation of vouchers.

Unblinding will occur after database lock and finalization of this SAP.

## IV. ANALYSIS POPULATIONS

- a. **Intention-to-Treat (ITT) Population:** All randomized participants will be included and analyzed according to their assigned treatment group, regardless of voucher or product use. The ITT population will serve as the primary analysis population.
- b. **Per-Protocol (PP) Population:** The PP Population will be determined by using a continuous measure of adherence to study protocol through reporting on the New York State Prescription Monitoring Program and through self-report questionnaires. PP analyses will be considered supportive.
- c. **Safety population:** All participants who redeemed at least one voucher or used study product.

## V. ENDPOINTS

- a. **Primary endpoint: Opioid analgesic use:** weekly cumulative dose of opioid analgesics over 14 weeks.
  - i. **Measurement instrument:** Reported opioid dispensed to New York State Prescription Monitoring Program
  - ii. **Timepoint:** at baseline and completion of randomized trial (14 weeks)

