## VI. SAMPLE SIZE AND POWER

- a. We based our power analysis on a difference of 10% change in opioid analgesic dose between randomization arms over 14 weeks, which is clinically meaningful.
- b. **Alpha level:** 0.05, two-tailed, and 0/167 to correct for multiple comparisons between four arms.
- c. **Power:** Our sample size estimates incorporate a statistical power of 80% and 90%
- d. **Assumptions:** 15% attrition
- e. **Target sample size:** 276 (69 per arm)

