## VII. STATISTICAL METHODS

- a. **Primary Outcome Analysis:** We will use linear mixed-effects regression analyses (SAS, PROC MIXED) to examine whether assignment to the randomized voucher intervention at enrollment (independent variable) is associated with changes over time in weekly cumulative dose of opioid analgesics in morphine milliequivalents (dependent variable). We will examine intervention and time effects, as well as intervention-by-time interactions. To account for within-participant correlation across repeated weekly observations, we will include a random intercept for participant. We will follow the intention-to-treat principle, including all randomized participants in their originally assigned treatment groups. We will include covariates that differ at baseline or potential moderators, including gender and age. We will use a two-sided alpha of 0.05 and 95% confidence intervals.
- b. **Secondary Outcomes:** Using a similar approach to Aim 1, we will examine whether the initial soft gel capsule dispensed product with different THC/CBD content leads to adverse events. Each adverse event will be included in a separate model. For dichotomous (e.g., cannabis use disorder) or continuous outcomes (e.g., ASI drug subscale score), we will use mixed-effects linear or logistic regression analyses, respectively (SAS, PROC MIXED or PROC NL MIXED) to examine intervention and time effects, as well as intervention-by-time interactions. We will repeat this model using the initial soft gel capsule dispensed product as an instrumental variable to analyze the average effect of each medical cannabis product among those who continued taking the original product. We will also repeat this model using alternative measures of medical cannabis (cumulative dose of THC and CBD).
- c. **Sensitivity Analyses:** To fully understand the intervention effect, we will also conduct per-protocol analyses. If key variables are unequally distributed among randomized arms, we will conduct adjusted analyses.

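### The primary analysis makes no stated use of prior opioid dose: the baseline window is undefined and the model names no pre-randomisation dose covariate

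*SAP*

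**What the plan says.** Section V.a defines the primary endpoint as "weekly cumulative dose of opioid analgesics over 14 weeks". Its source is given as "Reported opioid dispensed to New York State Prescription Monitoring Program" and its timing as "at baseline and completion of randomized trial (14 weeks". No length is given for the baseline period.

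Section III.b stratifies randomisation by chronic versus sporadic opioid use. Chronic use means "prescribed opioids for greater than or equal to 90 overlapping days in the past 182 days". The rule is about days prescribed, not dose, and no data source is named for it.

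Section VII.a fits a linear mixed model to weekly dose. For "within-participant correlation across repeated weekly observations" the plan states: "we will include a random intercept for participant". On adjustment it says: "We will include covariates that differ at baseline or potential moderators, including gender and age". Neither baseline dose, nor earlier dose, nor the stratification factors are named. The primary objective in II.a is a difference in cumulative dose at 14 weeks, and VI.a sizes the trial on "a difference of 10% change in opioid analgesic dose between randomization arms over 14 weeks".

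**The concern.** The trial mixes chronic and sporadic users, so usual weekly dose should be expected to differ widely between people. In a comparison of 14-week dose between arms of 69, that spread is likely to be the largest part of the error, and a person's own earlier dose is its natural predictor.

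The plan needs half a year of prescribing history to stratify, but the only stated product of that history is a two-level label. The label cannot separate low from high doses among chronic users. In a sporadic user, a short baseline window may contain no dispensing at all. As VII.a is worded, prior dose enters the model only if it happens to differ between arms or is counted as a moderator. At stake is the precision of the primary comparison, together with an open choice about how a primary-endpoint variable is derived.

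**Working it through.** **Inputs from the SAP.** Look-back 182/7 = 26 weeks (III.b); 14 post-randomisation weeks (V.a); random-intercept structure, which implies equal correlation between all weeks (VII.a); 276/4 = 69 per arm (VI.e). The SAP gives no standard deviation and no between-week correlation, so the sample size cannot be reproduced and the correlations below are assumptions.

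**Set-up.** Scale the total variance of one week's dose to 1. Let ρ be the share that is stable between people and 1 − ρ the within-person share. The quantity of interest is the residual variance of the mean of the 14 post-randomisation weeks after adjusting for pre-randomisation dose:

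residual variance = Var(14-week mean) − c′B⁻¹c,

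where B is the covariance matrix of the baseline summaries and c their covariance with the 14-week mean.

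**Equal correlation.**
- Unadjusted: (1 + 13ρ)/14.
- Adjusted for one baseline week: subtract ρ².
- Adjusted for that week and the 26-week mean: subtract 26ρ²/(1 + 25ρ) instead. Under equal correlation the single week adds nothing to the mean.

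For ρ = 0.5: (1 + 6.5)/14 = 0.5357. One week leaves 0.5357 − 0.25 = 0.2857. Both measures leave 0.5357 − 6.5/13.5 = 0.0542. The ratio is 0.0542/0.2857 = 0.19, so the standard error is multiplied by √0.19 = 0.44.

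**Results: residual variance with one week → with week plus 26-week mean (reduction).**

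| Assumed structure | ρ = 0.3 | ρ = 0.5 | ρ = 0.7 | ρ = 0.9 |
|---|---|---|---|---|
| Equal correlation | 0.2600 → 0.0747 (71%) | 0.2857 → 0.0542 (81%) | 0.2314 → 0.0328 (86%) | 0.0971 → 0.0110 (89%) |
| Half of within-person variance AR(1) at 0.8 per week, half independent | 0.3252 → 0.2206 (32%) | 0.3068 → 0.1645 (46%) | 0.2288 → 0.1010 (56%) | 0.0912 → 0.0341 (63%) |
| All within-person variance AR(1) at 0.9 | 0.3355 → 0.3217 (4%) | 0.2651 → 0.2417 (9%) | 0.1743 → 0.1503 (14%) | 0.0632 → 0.0515 (18.5%) |

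With pure AR(1) at 0.90 or 0.95 and no stable person effect, the reduction is nil.

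**Why both measures.** Under strong autocorrelation the 26-week mean alone does worse than the last week alone: 1.21 to 1.40 times the variance in the third row of the table, and 1.45 and 1.80 times under pure AR(1) at 0.90 and 0.95. Using both cannot raise the residual variance; the only price is the degrees of freedom.

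**If baseline already means a longer window.** Adding the 26-week mean to a 4-week mean cuts variance by 53% to 65% under equal correlation and 19% to 38% under partial decay. Added to a 13-week mean, it cuts it by 22% to 26% under equal correlation.

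**The arm-by-time slope.** The same two covariates, applied to each person's weekly slope after randomisation, give variance ratios of 1.00 under equal correlation, 0.99 to 0.95 under partial decay and 0.98 to 0.88 with all within-person variance AR(1) at 0.9.

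**The case against.** The strongest case on the other side has five parts.

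- **Baseline is not said to be one week.** A reader might infer from a weekly endpoint and a single timepoint that the plan fixes one week and throws 26 away. The SAP does not say so: a week, a month or 182 days would all fit. This stands. What the document supports is that the window is undefined and that no use of prior dose is stated.
- **The history is not shown to be free.** A reader might infer that weekly doses for the past 182 days are already in hand. III.b counts prescribed days and names no source, and V.a.i ties the registry to the outcome only. This stands. The cost is probably low, but the extract must be checked.
- **The gain may not reach the tested contrast.** VII.a models change over time and arm-by-time interactions without saying which term is primary. Time-constant covariates explain a person's level, which a within-person slope is already free of. This stands for the slope. A larger slope gain (variance ratio about 0.38 to 0.50) appears only if the pre-randomisation weeks are modelled as rows with a flat pre-period, which is a different analysis. For the dose-level contrast, which is what II.a asks about, the gain remains.
- **The comparator is itself assumed.** The reductions are measured against a model with one baseline week, which VII.a does not specify. Adjusting for the chronic-use stratum, also unstated, could capture part of the gain already.
- **Omitting a precision covariate is not an error.** It is true that nothing here is biased. But the plan leaves the baseline of its primary endpoint undefined and makes adjustment depend on observed imbalance, which is a poor way to fix the most predictive covariate it could have.

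**Conclusion.** The point holds as one of lost precision and incomplete specification. The SAP leaves the baseline dose window undefined and makes no stated use of prior dose in the primary model, although it needs a 26-week prescribing history for stratification and draws its outcome from a dispensing registry.

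The benefit of using that history for the 14-week dose-level contrast ranges from none to 89% less residual variance, depending on correlations that the SAP does not report. The top of the range (71% to 89%) belongs to the SAP's own random-intercept structure with baseline taken as one week. Weekly dispensing whose correlation decays over time would give less. A reader should not infer that a large gain is assured, that it extends to the arm-by-time slope, or that the planned estimate is biased; the document supports none of these. The change is worth making because it costs little and, in every case examined, using both measures lost no precision.

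**What to change.** Section I places the SAP before unblinding and database lock, so the change can still be prespecified.

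1. In V.a.ii, define two pre-randomisation measures from the same registry as the outcome: a recent baseline dose (for example the last week before randomisation) and the mean weekly morphine-equivalent dose over the 182 days before randomisation.
2. In VII.a, enter both as fixed covariates whatever the observed balance, and state that they serve the 14-week dose-level contrast between arms.
3. Confirm that the registry extract reaches back 182 days and holds dose, not only days prescribed.

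The cost is about one sentence in each of the two sections, one derived variable beyond the baseline dose, two degrees of freedom among 276 participants, and the check in step 3. No new participant contact is implied if the extract reaches back far enough.

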## VI. SAMPLE SIZE AND POWER

- a. We based our power analysis on a difference of 10% change in opioid analgesic dose between randomization arms over 14 weeks, which is clinically meaningful.
- b. **Alpha level:** 0.05, two-tailed, and 0/167 to correct for multiple comparisons between four arms.
- c. **Power:** Our sample size estimates incorporate a statistical power of 80% and 90%
- d. **Assumptions:** 15% attrition
- e. **Target sample size:** 276 (69 per arm)

## VII. STATISTICAL METHODS

- a. **Primary Outcome Analysis:** We will use linear mixed-effects regression analyses (SAS, PROC MIXED) to examine whether assignment to the randomized voucher intervention at enrollment (independent variable) is associated with changes over time in weekly cumulative dose of opioid analgesics in morphine milliequivalents (dependent variable). We will examine intervention and time effects, as well as intervention-by-time interactions. To account for within-participant correlation across repeated weekly observations, we will include a random intercept for participant. We will follow the intention-to-treat principle, including all randomized participants in their originally assigned treatment groups. We will include covariates that differ at baseline or potential moderators, including gender and age. We will use a two-sided alpha of 0.05 and 95% confidence intervals.
- b. **Secondary Outcomes:** Using a similar approach to Aim 1, we will examine whether the initial soft gel capsule dispensed product with different THC/CBD content leads to adverse events. Each adverse event will be included in a separate model. For dichotomous (e.g., cannabis use disorder) or continuous outcomes (e.g., ASI drug subscale score), we will use mixed-effects linear or logistic regression analyses, respectively (SAS, PROC MIXED or PROC NL MIXED) to examine intervention and time effects, as well as intervention-by-time interactions. We will repeat this model using the initial soft gel capsule dispensed product as an instrumental variable to analyze the average effect of each medical cannabis product among those who continued taking the original product. We will also repeat this model using alternative measures of medical cannabis (cumulative dose of THC and CBD).
- c. **Sensitivity Analyses:** To fully understand the intervention effect, we will also conduct per-protocol analyses. If key variables are unequally distributed among randomized arms, we will conduct adjusted analyses.

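### The primary model handles repeated weekly doses with a random intercept only, so the intervention-by-time test can exceed 5% if doses are serially correlated or participants' trends differ

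*SAP*

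**What the plan says.** Section VII.a plans a linear mixed model in PROC MIXED for "changes over time in weekly cumulative dose of opioid analgesics in morphine milliequivalents (dependent variable"). On the effects of interest it says: "We will examine intervention and time effects, as well as intervention-by-time interactions". On correlation it says: "To account for within-participant correlation across repeated weekly observations, we will include a random intercept for participant". On inference it says: "We will use a two-sided alpha of 0.05 and 95% confidence intervals".

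The random intercept is the only stated device for within-participant correlation. The SAP names no random slope, residual structure, empirical standard error or degrees-of-freedom method, and gives no variance or correlation figure. It does not say whether time is linear or categorical.

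Section V defines the endpoint as "weekly cumulative dose of opioid analgesics over 14 weeks", taken from dispensing records ("Reported opioid dispensed to New York State Prescription Monitoring Program"), but gives the timepoints as "at baseline and completion of randomized trial (14 weeks"). Section VIII pools imputed datasets by Rubin's rules.

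**The concern.** A random intercept with independent residuals implies compound symmetry: weeks 1 and 2 are as strongly correlated as weeks 1 and 14, and participants in an arm differ in level but not in trend. Opioid dose may well break both assumptions. Adjacent weeks can be covered by the same prescription. The trial also enrols both chronic and sporadic opioid users (a stratification factor in section III), who need not change at one common rate.

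Section VII.a asks about change over time, so the intervention-by-time term carries much of the primary question. It is also the term whose standard error depends most on the covariance model. If that standard error is too small, the 95% intervals undercover and a positive interaction may be an artefact. The sensitivity analyses in section VII.c are per-protocol and covariate-adjusted, and neither would reveal the problem.

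**Working it through.** **Inputs from the SAP.** Weekly observations over 14 weeks (T = 14, inferred), random intercept only, two-sided alpha 0.05, 69 per arm (4 × 69 = 276). The SAP has no covariance figure to reproduce. Every covariance value below is an assumption.

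**Method.** Take balanced data and linear time. Let t be the centred week number, so Sxx = Σt² = 227.5, and let S be the true covariance matrix of one participant's 14 values.

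- True variance of a participant's slope: t′St / Sxx².
- Variance used by the random-intercept model: s² / Sxx, where s² is the mean within-participant variance, trace(PS)/13, and P removes the participant mean.
- Ratio R = t′St / (Sxx × s²).
- Pairwise type I error: 2 × [1 − Φ(1.96/√R)]. Overall four-arm interaction: P(χ²₃ > 7.815/R).

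Sample size cancels from R, so a larger trial does not cure the problem.

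**Example 1, AR(1) = 0.5, residual variance 1.** t′St = 495.5 and s² = 0.868, so R = 495.5 / (227.5 × 0.868) = 2.51. Then 1.96/√2.51 = 1.24, and type I error is 21.6%.

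**Example 2, differing slopes.** Between-person SD 1, residual SD 0.5, SD of change from week 1 to week 14 equal to 0.5. Slope variance = (0.5/13)² = 0.00148. True variance = 0.00148 + 0.25/227.5 = 0.00258. Model s² = 0.25 + 0.00148 × 227.5/13 = 0.276, giving 0.276/227.5 = 0.00121. R = 2.13 and type I error is 17.9%.

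| Assumed structure (linear time) | R | Pairwise | Overall 3 df |
|---|---|---|---|
| Compound symmetry | 1.00 | 5.0% | 5.0% |
| AR(1) 0.2 | 1.42 | 10.0% | 13.8% |
| AR(1) 0.5 | 2.51 | 21.6% | 37.4% |
| AR(1) 0.8 | 4.91 | 37.7% | 66.2% |
| Slope SD 0.25 of between-person SD | 1.30 | 8.6% | 11.2% |
| Slope SD 0.5 | 2.13 | 17.9% | 29.9% |
| Slope SD 0.75 | 3.27 | 27.8% | 49.5% |
| Residual shared within 2-week fills | 2.13 | 18.0% | 30.0% |
| Residual shared within 4-week fills | 3.91 | 32.2% | 57.3% |
| Running total | 12.36 | 57.7% | 88.9% |

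For AR(1) 0.2, 0.5 and 0.8, correct intervals would be wider by √R = 1.19, 1.58 and 2.22. The running total is severe because summing turns each participant's level into a slope, so slopes differ by construction. That row assumes weekly dose variance split equally between participant and residual.

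**Cases where inflation is smaller, absent or reversed.**
- Two timepoints only: R = 1 exactly, so no inflation.
- Categorical time, overall 39-df test (3 × 13), simulated at 69 per arm: 6.3%, 8.4%, 12.7% and 17.6% for AR(1) 0.3, 0.5, 0.7 and 0.9; 25.2% for a running total.
- Four-week fills booked wholly in the week dispensed, simulated: about 0% for linear time (conservative), 17.2% for categorical time.
- Arm comparison of participant means over the weeks, simulated: 3.8% to 5.7% throughout.

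**After the change.** A test on participant-level slopes, equivalent for balanced data to a random-slope model, gave 4.2% to 5.8% in every simulated scenario (2,000 null trials each). Results at 58 per arm (69 less 15% attrition) were similar. Dropout and multiple imputation were not modelled.

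**The case against.** The strongest reply is that none of the inflation figures comes from the trial. The SAP states no correlation, slope variance, time coding or rule for allocating a fill to weeks, and several choices consistent with its text give little or no inflation. With categorical time and mild departures the overall test stays near 5% to 6%. A slope SD of only 0.25 residual SDs gives 5.9% even with linear time. If a fill is booked in the week it is dispensed, the linear-time test is conservative. The argument that weeks within a fill duplicate each other presupposes that fills are spread over their days of supply, which the SAP does not say. The SAP also does not make the interaction its sole primary test: section II frames the objective as a difference in cumulative dose from placebo, and the arm comparison averaged over weeks is sound.

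All of this stands, and it limits the claim. A reader might infer that the standard errors are certainly too small, that the false-positive rate is certainly well above 5%, or that the whole primary analysis is invalid. The document supports none of these.

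The two-timepoint defence does not stand. Section V lists only baseline and 14 weeks, but section VII.a explicitly models repeated weekly observations, so the two sections conflict. The remaining escapes depend on choices that the SAP leaves unstated.

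**Conclusion.** The point holds conditionally. Section VII.a names a random intercept as the sole provision for correlation, and the validity of the intervention-by-time test then rests on compound symmetry that nothing in the SAP supports. For linear time over 14 weeks, pairwise type I error is about 10% to 38% for AR(1) 0.2 to 0.8, about 9% to 28% for slope SDs of 0.25 to 0.75 of the between-person SD (residual SD 0.5), and about 58% for a running total. These results assume complete, balanced data and the covariance values shown. The size, and in one case the direction, of the error depends on time coding, outcome construction and fill allocation. What is established is that the planned test is unprotected against ordinary departures, not that it will fail.

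**What to change.** In section VII.a, before unblinding:

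1. Replace the random-intercept-only model with a random intercept and random slope for time, serially correlated residuals (for example AR(1)), or both. Alternatively keep the intercept and use empirical (sandwich) standard errors clustered on participant. Prespecify a fallback for non-convergence. A fully unstructured matrix is a poor first choice: 14 weeks need 14 × 15/2 = 105 covariance parameters.
2. Make the standard errors and degrees of freedom compatible with the Rubin's-rules pooling in section VIII. Kenward-Roger degrees of freedom do not carry directly through that pooling.
3. State whether time is linear or categorical, and whether the outcome is each week's dose or a running total.
4. Reconcile the two timepoints in section V with the weekly observations in section VII.a.
5. Keep the random-intercept-only model as a sensitivity analysis.

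The cost is a few lines of SAS and SAP text, and wider confidence intervals where the simpler model was wrong. Making the choice before unblinding avoids a covariance structure selected on the results.

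### The primary model chooses covariates by observed baseline imbalance and does not fix the three randomisation strata in advance, so whether and how the primary result is adjusted is left open

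*SAP*

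**What the plan says.** Section VII.a describes a linear mixed model for weekly opioid dose. On its terms it says "We will examine intervention and time effects, as well as intervention-by-time interactions", and for the correlation of repeated measures "we will include a random intercept for participant". The covariate rule is one sentence: "We will include covariates that differ at baseline or potential moderators, including gender and age".

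Section VII.c, under sensitivity analyses, adds: "If key variables are unequally distributed among randomized arms, we will conduct adjusted analyses".

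Section III.b describes the randomisation: "We stratified by history of cannabis use (cannabis naïve, non-daily cannabis use, daily cannabis use), baseline opioid use" (chronic or sporadic) and "primary pain condition (neuropathic versus non-neuropathic pain". No section says that these factors enter the primary model.

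Section V.a gives the timing of the primary endpoint as "at baseline and completion of randomized trial (14 weeks". Baseline dose is therefore measured, but the SAP does not say how it is used in the model.

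**The concern.** In a randomised trial, a baseline difference between arms arises by chance. It does not show that the variable predicts the outcome, and predicting the outcome is what makes adjustment useful. A rule that admits covariates because they differ has two consequences.

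- **The primary model depends on the data.** What counts as differing, and among which variables, is left to whoever runs the analysis. The wording does not settle whether gender and age always enter or are only examples.
- **The rule tends to leave out the wrong variables.** Stratified randomisation keeps cannabis history, opioid chronicity and pain type close to balanced, so they are unlikely to qualify. Yet opioid chronicity is plausibly strongly related to weekly opioid dose.

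VII.a and VII.c also apply the same trigger to analyses of different rank. A reader cannot tell whether the primary estimate is adjusted with an unadjusted check, or the reverse.

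Finally, entering a potential moderator as a covariate adjusts for it. It does not test moderation.

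**Working it through.** **Inputs from the SAP.** Strata: 3 × 2 × 2 = 12 (III.b). Target: 276, or 69 per arm, with 15% attrition (VI). Two-sided alpha 0.05 (VII.a). The SAP gives no standard deviation, no within-person correlation and no share of variance explained by the strata. The 276 can therefore be neither reproduced nor refuted, and every size below rests on a stated assumption.

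**1. How often chance alone would change the model.** Assume that differing means p < 0.05 and that k candidate variables are independent. The probability that at least one enters is 1 − 0.95^k:

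| k | Probability |
|---|---|
| 3 | 14% |
| 5 | 23% |
| 10 | 40% |
| 20 | 64% |

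The SAP gives neither k nor the threshold, so the range is the result.

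**2. Level or week-14 contrast with the strata omitted.** Let R² be the share of outcome variance explained by the strata (assumed 0.2 to 0.5). With near-perfect stratum balance, the true sampling error of the contrast contains no stratum variance, but the unadjusted model's standard error does. It is too large by the factor c = 1/√(1 − R²), and the actual type I error is 2 × [1 − Φ(1.96c)].

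| R² | c | Actual type I error (nominal 5%) |
|---|---|---|
| 0.2 | 1.12 | 2.8% |
| 0.3 | 1.20 | 1.9% |
| 0.5 | 1.41 | 0.6% |

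These are upper bounds on the effect. A target of 276 over 12 strata is 276/12 = 23 participants per stratum on average, or 23/4 = 5.75 per arm within a stratum. The SAP gives no block size, so incomplete blocks could leave the balance short of perfect.

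**3. Power for the same contrast, R² = 0.3, alpha 0.05.** The answer depends on which standard deviation lay behind the 276.

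- Sized at 80% on the ordinary unadjusted standard deviation: unadjusted power is Φ[(1.96 + 0.84) × 1.195 − 1.96 × 1.195] = Φ(1.01) = 84%. Adjusted power is Φ[(1.96 + 0.84) × 1.195 − 1.96] = Φ(1.39) = 92%.
- Sized at 80% on the standard deviation left after stratum adjustment: unadjusted power is Φ[(1.96 + 0.84) − 1.96 × 1.195] = Φ(0.46) = 68%.

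Section VI does not say which applies.

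**4. Intervention-by-time slope.** With complete data and a random intercept, the slope contrast is estimated from each participant's deviations from his or her own mean. A covariate that is constant over time cancels from those deviations. Random-intercept models fitted to assumed data (two strata 1.5 between-person standard deviations apart) show this:

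| Standard error of | Without stratum | With stratum |
|---|---|---|
| Arm-by-time slope, baseline week included | 0.01286 | 0.01286 |
| Arm-by-time slope, post-baseline weeks only | 0.0143 | 0.0143 |
| Arm level, post-baseline weeks only, no interaction | 0.2514 | 0.2123 |

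The level contrast improves (0.2514/0.2123 = 1.18) and the slope does not. Adding baseline dose as a covariate also left the post-baseline slope standard error at 0.0143.

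**The case against.** The strongest counter-argument is that the planned model is about change over time. If week 0 is in the outcome vector and time is coded from baseline, the intervention-by-time term carries the treatment effect, and the random intercept already absorbs stable differences between participants. This stands. On that reading, omitting the strata as main effects costs essentially no precision, and because the SAP names no primary contrast, that reading cannot be excluded.

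A reader might infer that power falls from 80% to 68%. The documents do not support this. It requires that 276 was derived from a stratum-adjusted standard deviation, and section VI gives no standard deviation at all. With an ordinary one, what is lost is extra power (84% against 92% at R² = 0.3), not planned power. The type I error shifts in the conservative direction, so validity is not threatened.

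A reader might also infer that baseline dose is left out of the model. That is not established either. Sections V.a and VII.a are compatible with baseline being the week-0 outcome. What can be said is that its role is not stated.

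Two further points stand in part. The phrase about potential moderators is an open list through which the stratification factors could enter; they are not excluded, only not prespecified. And section XII states that the statisticians are blinded, which limits covariate choice driven by the treatment effect. It does not make the model fixed: arms can be compared under coded labels, and the covariate set would still follow from what is seen.

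**Conclusion.** The point holds in a limited form. Whichever contrast is primary, three things are true on the text: covariates are admitted by observed imbalance with no list, test or threshold; VII.a and VII.c leave open whether the primary result is adjusted; and the randomisation strata are not prespecified in the model and would tend to be screened out.

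The statistical cost is conditional. For a level or week-14 contrast it is a conservative test and forgone precision, of at most the size shown in step 2 and resting on an assumed R² of 0.2 to 0.5 and near-perfect balance. For the slope contrast it is essentially nil. No loss of planned power can be claimed from this document. The change should be made because it is nearly free and removes an avoidable choice from the primary analysis, not because the trial is shown to be underpowered.

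**What to change.** Before unblinding:

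1. Replace the covariate sentence in VII.a with a fixed set: the three stratification factors as randomised, plus age and gender if wanted. State that no covariate is added or dropped because of observed baseline differences.
2. Name the primary contrast (level, week 14 or intervention-by-time slope).
3. State the role of baseline weekly opioid dose. Use it as a covariate only if week 0 is not in the outcome vector; otherwise model it as the week-0 outcome. Doing both would put it on both sides of the model.
4. Give any adjusted sensitivity analysis in VII.c a fixed covariate list, or delete it.
5. Examine moderators only through arm-by-moderator interactions, labelled exploratory.

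The cost is SAP wording and a few degrees of freedom: 2 + 1 + 1 = 4 for the stratification factors as main effects, and a small number more for age and gender. The stratification factors had to be known in order to randomise, so they need no new data.
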